## 9.4 Data Source

Data on patients will be obtained from primary care outpatient anonymised clinical records, dispensation in pharmacies of primary care prescriptions and diagnosis at hospital discharge from the Spanish public National Health System (SNS). Those data banks are unified in the data source so-called "Base de datos para la investigación Farmacoepidemiológica en Atención Primaria" (BIFAP) (8,9).

BIFAP includes information about patients' age, sex, life-style factors (i.e. body mass index (BMI), smoking status, alcohol consumption), clinical events (recorded by using

the International Classification of Primary Care (ICPC) and the International Classification of Diseases 9th Revision (ICD-9) medical terms (6,7)), anonymised primary care physicians' (PCPs) free-text notes, specialist referrals and discharge letters, prescriptions issued in primary care and their dispensations in pharmacies, vaccinations, laboratory test results and diagnosis at hospital discharge (recorded through the RAE-CMBD system) of around 13.7 million patients attended in a public primary care setting (7.4 of them aged  $\geq 18$  years). BIFAP covers 7 out of 19 districts in Spain and 57% of their population overall (as described in the Spanish Statistical Office (10)). In addition, currently, data on covid-19 infections resulting in an admission or discharge diagnosis to hospital (inpatient record) or intensive care unit as the setting of care are being incorporating to BIFAP. Figure 2:

BIFAP is fully funded by the Spanish Agency on Medicines and Medical Devices (AEMPS), belonging to the public Department of Health, and is maintained with the collaboration of the participant regions (8).

The records on the results of the COVID-19 laboratory test will be linked with BIFAP primary care profiles. Also, all vaccinations administrated against COVID-19 recorded in any setting will be linked with the primary care history in regions providing data. Particularly, vaccinations will be entered in the BIFAP's Table of Vaccines that in 2019 included around 61 million of recorded vaccinations.

BIFAP has been previously validated for research in pharmacoepidemiology, including the estimations of the precision of several clinical outcomes (9,11–13) that will be covariates of the current study (such as cardiovascular/digestive/endocrinological outcomes). Also, vaccination recorded in BIFAP's Table of Vaccines has also been confirmed valid through formal precision studied or against external comparable data sources (3,4).

## 9.5 Study Size

All patients meeting the eligibility criteria in BIFAP will be included as source population. BIFAP includes information of around 7.7 million patients aged  $\geq 18$  years (as last updated version in 2018), which distribution by sex and age is as follows:

	TOTAL	18 - 19	20 - 24	25 - 29	30 - 34	35 - 39	40 - 44	45-49	50 - 54	55-59	60-64	65-69	70-74	75-79	80-84	85-89	90-110
TOTAL	7720843	252143	424740	465933	526002	647688	747020	717918	702323	658868	569616	493770	454787	350359	317844	246643	145189
Women	3991612	122805	209807	232836	265565	324008	369475	357547	352106	330858	290309	255848	242742	194252	187908	154500	101046
Men	3729231	129338	214933	233097	260437	323680	377545	360371	350217	328010	279307	237922	212045	156107	129936	92143	44143

Taking into account the estimated COVID vaccine effectiveness reported in clinical trials [75-78], varying assumptions of vaccine unexposed to exposed ratio, anticipated global sample sizes of patients aged  $\geq 18$  years in BIFAP, a cumulative positive symptomatic COVID cases of 60,57 per 100,000 people in 14-days in Spain (as reported on 22 March 2021 [when started the vaccination for general people, i.e. apart from health workers and nursing home residents] in [www.cnecovid.isciii.es/covid19/](http://www.cnecovid.isciii.es/covid19/)), [33], the different probabilities that the upper limit of the 95% CI of the risk ratio (RR) being below 1.00 (a correlate of the lower bound of the vaccine effectiveness estimate being above 0.00 [Section 9.7.3.1] demonstrating a protective effect of vaccination) was estimated and displayed in Table 1:

**Table 1. Study Size Precision Estimates overall ages**

Type of vaccine	Expected Vaccine Effectiveness a	Expected Ratio of Vaccine Unexposed to Exposed	Expected Sample Size (Exposed + Unexposed)	Expected Risk of the Outcome in the Unexposed b	Probability of the Upper Limit of the 95% CI to Be Below 1.00
Pfizer/Biontech (BNT162b2)	95% (90.3-97.6) $\rightarrow$ RR=0.05	1:1	7,720,843 people	0.0006057	1
Pfizer/Biontech (BNT162b2)	95% (90.3-97.6) $\rightarrow$ RR=0.05	2:1	7,720,843 people	0.0006057	1

Moderna (mRNA-1273)	94.1% (89.3-96.8) → RR=0.059	1:1	7,720,843 people	0.0006057	1
Moderna (mRNA-1273)	94.1% (89.3-96.8) → RR=0.059	2:1	7,720,843 people	0.0006057	1
Oxford/Astrazeneca (ChAdOx1 nCoV-19)	70.4% (54.8-80.6) → RR=0.296	1:1	7,720,843 people	0.0006057	1
Oxford/Astrazeneca (ChAdOx1 nCoV-19)	70.4% (54.8-80.6) → RR=0.296	2:1	7,720,843 people	0.0006057	1
Janssen (we use the 14- days effectiveness against mild-severe for 1 dose)	66.9% (59.0-73.4) → RR=0.331	1:1	7,720,843 people	0.0006057	1
Janssen (we use the 14- days effectiveness against mild-severe for 1 dose)	66.9% (59.0-73.4) → RR=0.331	2:1	7,720,843 people	0.0006057	1

CI = confidence interval; RR = relative risk.

Source: Rothman, K. *Episheet: spreadsheets for the analysis of epidemiologic data*. 2015. Available at: <http://www.krothman.org/episheet.xls>. Accessed March 2021.

a Vaccine effectiveness measured as 1 minus the RR, where the RR compared the risk of the outcome in vaccine-exposed versus that in unexposed individuals (i.e., an RR below 1 indicates a protective effect of the vaccine, corresponding to positive vaccine effectiveness).

b Cumulative symptomatic COVID cases of 60,57 per 100,000 people in 14-days in Spain (as reported on 22 March) expressed as cases per person in population without scaling.

Similarly, by age group the probabilities estimated were 1 (Table 2):

**Table 2. Study Size Precision Estimates by age categories**

Type of vaccine	Expected Vaccine Effectiveness a	Expected Ratio of Vaccine Unexposed to Exposed	Expected Sample Size (Exposed + Unexposed)	Expected Risk of the Outcome in the Unexposed b	Probability of the UL95% CI to Be <1.00
Pfizer/Biontech 16-55 years	95.6% (89.4-98.6) → RR= 0.044	1:1	4,483,767 people	0.0723	1
Pfizer/Biontech ≥55 years	93.7% (80.6-98.8) → RR= 0.063	1:1	3,237,076 people	0.0562	1
Pfizer/Biontech 16-55 years	95.6% (89.4-98.6) → RR= 0.044	2:1	4,483,767 people	0.0723	1
Pfizer/Biontech ≥55 years	93.7% (80.6-98.8) → RR= 0.063	2:1	3,237,076 people	0.0562	1
Moderna 18-65 years	95.6% (90.6-97.9) → RR=0.044	1:1	5,712,251 people	0.0697	1
Moderna ≥65 years	86.4% (61.4-95.2) → RR=0.136	1:1	2,008,592 people	0.0531	1
Moderna 18-65 years	95.6% (90.6-97.9) → RR=0.044	2:1	5,712,251 people	0.0697	1
Moderna ≥65 years	86.4% (61.4-95.2) → RR=0.136	2:1	2,008,592 people	0.0531	1
Janssen* 18-59 years	63.7% (53.9-71.6)→ RR=0.363	1:1	5,142,635 people	0.0710	1
Janssen ≥60 years	76.3% (61.6-86.0)→ RR=0.237	1:1	2,578,208 people	0.0543	1
Janssen 18-59 years	63.7% (53.9-71.6)→ RR=0.363	2:1	5,142,635 people	0.0710	1
Janssen ≥60 years	76.3% (61.6-86.0)→ RR=0.237	2:1	2,578,208 people	661,162/12,186,162=0.0543	1

The probabilities were calculated based on the following effectiveness reported in the clinical trials by age groups:

**Pfizer/Biontech (BNT162b2) [75]:**

1. 16-55 years: 5 cases (0,05%) de 9897 vaccinated and 114 cases (1,145%) among 9955 in comparison group. Efficacy: 95,6% (89,4-98,6)
2. >55 years: 3 cases (0,04%) de 7500 vaccinated and 48 cases (0,636%) among 7543 in comparison group. Efficacy: 93,7% (80,6- 8,8)
3. ≥65 years: 1 case (0,025%) de 3848 vaccinated and 19 cases (0,489%) among 3880 in comparison group. Efficacy: 94,7% (66,7- 99,9)

4. ≥75 years: 0 cases among 774 vaccinated and 5 cases (0,636%) among 785 in comparison group. Efficacy: 100% (-13,1 – 100)

**Moderna (mRNA-1273)** [76]:

1. ≥18-65 years: 7 cases (0,066%) de 10551 vaccinated and 156 cases (1,482%) among 10521 in comparison group. Efficacy: 95,6% (90,6-97,9).
2. ≥65 years: 4 cases (0,111%) de 3583 vaccinated and 29 cases (0,816%) among 3552 in comparison group. Efficacy: 86,4% (61,4-95,2)

**Janssen** (efficacy 14 days to COVID-19 mild-severe, 1 dose) [78]:

1. ≥18-59 years: 95 cases among 12750 vaccinated and 260 cases among 12782 in comparison group. Efficacy: 63,7% (53,9-71,6).
2. ≥60 years: 21 cases among 6764 vaccinated and 88 cases among 6762 in comparison group. Efficacy: 76,3% (61,6-86,0).

\*Note: for Oxford/Astrazeneca vaccine no efficacy was published by age groups. The published efficacy referred mainly to individuals aged 18-55 years although also 12% of participants were ≥56y [77].

Regarding children and adolescents, 1.6 million patients aged 0-17 years are registered in the data source distributed by age and sex as follows:

	TOTAL	0	1	2	3	4	5	6	7	8	9	10	11	12	13	14	15	16	17
TOTAL	1598371	131318	72389	77656	80082	81668	81753	86036	89054	90738	92347	95206	91962	90963	89196	88696	88560	85602	85145
Women	777196	63920	35333	37770	38976	39282	39612	41726	43396	44264	44783	46103	44623	44141	43534	42939	43432	41749	41613
Men	821175	67398	37056	39886	41106	42386	42141	44310	45658	46474	47564	49103	47339	46822	45662	45757	45128	43853	43532

Since no information about the efficacy has been provided yet for younger than 16 or 18 years (according to the vaccines), probability of the upper limit of the 95% confidence interval to be < 1.00 will be calculated ah-hoc in case of approval vaccinations among children and adolescents.

## **9.6 Data Management**

The necessary data to implement this study from each included data source will be extracted by BIFAP's IT through programming and/or epidemiologists through BIFAP specific applications.

Previous to that the different registries will be linked to primary care histories by the local government teams of regions participating in BIFAP. Those pseudonymised individual-level will be sent to BIFAP IT and held at the AEMPS research sites. The Governance of data use is publicly available [68].

STATA will be used as statistic analytic program.

## **9.7 Data Analysis**

### **9.7.1 Descriptive Characteristics**

The distributions of baseline characteristics by exposure group/periods will be calculated to describe the study cohorts and illustrate differences between the groups compared. For continuous variables, means, standard deviations, medians, and interquartile ranges will be estimated. For categorical variables, counts and proportions will be estimated. The missingness of variables such as BMI, smoking status and alcohol use among other will also be described.

### **9.7.2 Incidence Analysis**

The crude incidence rates of the COVID-19 outcomes will be estimated after time zero for the vaccinated and unvaccinated groups for each brand.

Additionally, each vaccination strategy (e.g., fully completed on time, partially completed, delayed completion; see Section 9.3.1 and **iError! No se encuentra el origen de la referencia.**), for the same brand will be considered a separate exposure group and compared to unvaccinated.

Crude incidence rates (with 95% CI) will be estimated using the number of outcome events as the numerator and the number of person-years of follow-up as the denominator for the study periods defined.

Additionally, cumulative incidence curves (1 minus the Kaplan–Meier risk) for outcomes will be estimated to visualise the occurrence of COVID-19 outcomes over time since time zero [38].

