#### **9.1.1.4 Definition of Time Zero**

In studies of vaccinated versus unvaccinated persons, researchers must determine the appropriate time point at which to identify patients and begin follow-up. Aligning the evaluation of eligibility criteria, covariate assessment, exposure assignment, and beginning of follow-up (time zero) avoids selection bias and immortal person-time bias and addresses a well-defined study question [13].

Time zero is the time when the vaccination status is assigned; all eligibility criteria must be fulfilled at that point, and COVID outcomes must start to be counted at that point [14].

Time zero in the vaccinated group will be the date when the 1st dose of COVID-19 vaccine is administered (i.e. recorded). That date will be also used for the unvaccinated pairs as Time zero.

The aim of the **Main analysis** will be the estimation of the effectiveness  $\geq 15$  days after full vaccination series whether 1- or 2-doses regimens (and regardless of delayed completion of 2-dose vaccine series ,i.e. recorded dates will be accepted as real world data even though the time between doses are not fully adjusted to recommended intervals). Analysis will be performed by vaccine brand.

In order to properly observe the moment when the effect of the vaccination starts, the period between 1st Dose and 14 days after the 2nd dose will be divided and compared with unvaccinated patients. Thus, at least 5 cut-of periods will be identified along each patient's follow-up contribution:

- 1) Non-exposed period among Unvaccinated patients (Reference for Effectiveness estimation)

- 2) D1-induction time: up-to 14 days after 1st dose
- 3) D1-effectiveness: 15 days after 1st dose to 2nd dose
- 4) D2-induction time: up-to 14 days after 2nd dose
- 5) D2-effectiveness in the short run: 15-90 days after 2nd dose
- 6) D2-effectiveness in the medium run: 91-180 days after 2nd dose
- 7) D2-effectiveness in the long run:  $\geq 181$  days after 2nd dose

[figure not shown]

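### Section 9.7.2 compares completion strategies from the first dose, although on-time, delayed or partial status is known only later, and gives no date from which a label starts

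*Protocol*

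**What the plan says.** Section 9.7.2 opens with the rule for the rates: "The crude incidence rates of the COVID-19 outcomes will be estimated after time zero for the vaccinated and unvaccinated groups for each brand". It then introduces "each vaccination strategy (e.g., fully completed on time, partially completed, delayed completion", and says that each of these "for the same brand will be considered a separate exposure group and compared to unvaccinated". The denominator is "the number of person-years of follow-up as the denominator for the study periods defined". Cumulative incidence curves are planned to "visualise the occurrence of COVID-19 outcomes over time since time zero".

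Section 9.1.1.4 places time zero at the first recorded dose, shares that date with the matched unvaccinated people, and defines it as the moment when vaccination status is assigned. It gives the reason: "Aligning the evaluation of eligibility criteria, covariate assessment, exposure assignment, and beginning of follow-up (time zero) avoids selection bias and immortal person-time bias".

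Section 9.3.1 lists COVID-19 infection among the events that end contribution. Section 9.7.2 cross-refers to 9.3.1 for the strategies, but 9.3.1 does not define them. The second cross-reference in the same sentence is broken.

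**The concern.** On the day of the first dose nobody can be classed as on time, delayed or partial. A person infected before dose 2 stops contributing and can only ever be a partial recipient. If the strategy label reaches back over the time between the doses, the completed groups are credited with event-free days that they had to survive to earn the label. The partial group receives every early infection.

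The two errors push in opposite directions. On-time and delayed completion would look better than they are, and the longer the delay, the larger the false gain. One dose alone would look ineffective or harmful. Readers would turn to this comparison for exactly those questions.

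**Working it through.** **Plan's own figure.** The protocol gives none for the strategy groups. Tables 1 and 2 concern vaccinated against unvaccinated people and do not bear on this point.

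**Inputs**
- Interval between doses, I: 21 or 28 days (section 9.3.1).
- Follow-up after dose 2, T: not given, so assumed. 90 and 180 days match the ends of two windows in 9.1.1.4; 30 and 60 days show shorter follow-up.
- Incidence: 60.57 per 100,000 in 14 days (section 9.5), so λ = −ln(1 − 0.0006057)/14 = 4.33 × 10⁻⁵ per day, taken as constant.
- Vaccine effect: none, so that any apparent effectiveness is bias.
- Infection ends contribution. Section 9.3.1 literally speaks of the last of the listed events. I read it as the first, in line with 9.3.3.2 and 9.3.3.3, which stop people at the COVID date.

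**Completers, label fixed at dose 1 and follow-up pooled.** Events can occur only in the T days after dose 2, but the denominator is T + I days. At this low incidence λ cancels:

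rate ratio = T/(T + I), so spurious effectiveness = 1 − T/(T + I) = I/(T + I).

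| T (days) | I = 21 | I = 28 |
|---|---|---|
| 30 | 21/51 = 41.2% | 28/58 = 48.3% |
| 60 | 21/81 = 25.9% | 28/88 = 31.8% |
| 90 | 21/111 = 18.9% | 28/118 = 23.7% |
| 180 | 21/201 = 10.4% | 28/208 = 13.5% |

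The exact constant-hazard calculation with the λ above agrees within 0.1 percentage point at T = 90 and T = 180. For delayed completion, an assumed interval of 42 days gives 42/132, about 32%, at T = 90 and 42/222, about 19%, at T = 180. A longer delay therefore looks better with no true effect.

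**Partial group, same reading.** Let a share f complete if uninfected (assumed 80% or 90%), with everyone else followed for T + I days. The partial group holds the never-completers plus all infections before dose 2, and those infected people add almost no person-time:

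rate ratio ≈ 1 + f·I/[(1 − f)(T + I)].

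At T = 90:
- f = 0.8: 1 + 4 × 21/111 = 1.76 (I = 21) and 1 + 4 × 28/118 = 1.95 (I = 28).
- f = 0.9: 1 + 9 × 21/111 = 2.70 and 1 + 9 × 28/118 = 3.14.

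**Rates split by the defined periods.** Windows that start at or after dose 2 contain no time before dose 2, so the null rate ratio is 1.00. In the windows between dose 1 and dose 2, a group labelled by later completion still has zero events, whatever the vaccine does.

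**Status updated as time accrues.** The null rate ratio is 1.00 in every window.

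**The case against.** The strongest reply is that 9.7.2 never says the label is fixed at the first dose. It ties the rates to the defined study periods, and those periods cut follow-up at each dose. Exposure is updated over time elsewhere: comparators vaccinated later move to the vaccinated group from that date (9.3.1), and people who receive a second brand count as switchers from the date of that dose (9.7.3.2). Section 9.3.1 also plans to describe dose intervals before setting cut-off points, and such detail often sits in an analysis plan. The strategy contrast is an additional item in the incidence section, is not among the objectives in section 8, and is not used in the main analysis, which accepts delayed completion.

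Much of this stands. A reader might infer that immortal time enters every strategy comparison, but the text does not support that. Windows from dose 2 onward are free of it, the partial group suffers from excess events rather than immortal time, and a one-dose vaccine has no completion interval. Nor does the text say that the curves will be drawn by strategy. The pooled figures also depend on T and shrink as follow-up lengthens.

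It does not remove the point. The switcher rule and the Cox windows state when a status begins; the strategy groups have no such date. The listed periods contain no on-time, delayed or partial category, so splitting by period does not settle it. What 9.7.2 does state, groups named by later completion and rates from the first dose, is at odds with 9.1.1.4.

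**Conclusion.** The point holds in limited form. As written, 9.7.2 defines exposure groups by later events and estimates from time zero, against the protocol's own alignment rule. The harm falls on two-dose vaccines, wherever a strategy label covers person-time before dose 2: the windows between the doses, any pooled rate from dose 1, and any strategy-specific curve from time zero.

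If labels are fixed at dose 1 and follow-up is pooled, a null vaccine shows a spurious effectiveness in completers of about 19–24% with 90 days after dose 2 and about 10–13% with 180 days, and more with shorter follow-up. The partial group shows a false excess, with a rate ratio of roughly 1.8 to 3.1 at 90 days if 80–90% complete. These sizes rest on constant incidence, the 21- or 28-day interval, and assumed follow-up and completion shares.

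The main period-specific Cox analysis is not affected and no stated objective rests on this contrast. The text should be corrected, but the primary result is not in doubt on this account.

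**What to change.** State in 9.7.2 that strategy status is time-dependent:
- Person-time from dose 1 until dose 2 counts as one-dose.
- On-time or delayed status starts at the dose 2 date, according to the interval then observed.
- Overdue or partial status starts when the interval used for classification lapses without dose 2.

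Compare each status with unvaccinated person-time at the same time since the matched time zero, using the windows already defined. Draw any strategy-specific curves from the date the status starts. A landmark or a clone-censor-weight analysis would be an acceptable alternative. Repair the broken cross-reference and define the strategies where it points.

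The cost is a few sentences of protocol text. The time-splitting code is already needed for the Cox windows. The completed groups lose a little person-time.

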### 9.3.1 Exposure Assessment and Time At Risk

Data will be collected from BIFAP database with data from Spain (described in [Data Sources](#)).

**Inclusion criteria** to the Source population: up-to-standard,  $\geq 1$  year baseline information in January 2021 in BIFAP. The last date of filling all the inclusion criteria will be the inclusion date. No restriction to age or sex will be applied.

**Exclusion criteria:** Patients with prevalent COVID vaccinations or infections ever before (i.e. washout period) the inclusion criteria will be excluded.

**Stop date:** the last moment of the following criteria will define the stop date to contribution: covid-19 infection, death, loss to follow-up and end of study period (the last date available in the data source at data collection).

**Exposure assessment:** The 1st vaccination recorded after the inclusion date will be the time zero for patients included in the vaccinated group, as explained in section 'Definition of Time Zero' [9.1.1.4](#).

From the source population, 10 individuals unvaccinated on or before time zero of the vaccinated pair (10:1) will be randomly selected among those with similar birth cohort, sex and region (matched criteria). Patients included in the comparison group, may be vaccinated later during their follow-up period and then contribute to the vaccinated group (from the date of vaccine administration ahead; i.e. time zero for the vaccinated group).

\*Note: All individuals vaccinated during their follow-up contribution will be included in the vaccinated group. While, a random selection of the unvaccinated individuals will be included as unvaccinated group.

The date and type of vaccine administered will be collected from the **Table of Vaccine** from BIFAP data model. In particular, Covid-19 vaccinations will be ascertained from official covid-19 vaccination registries and provided by the regional governments. The coding system is not known yet. The feasibility analysis will include an evaluation of the coding type, whether or not vaccines are recorded according to standardised system or not. We expect that either ATC07 (J07????) or National Code (CNF [Código Nacional de

Farmacia]) specific for pharmaceuticals in Spain is available for all vaccines administered.

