#### **9.3.3.2 Symptomatic or Asymptomatic Diagnosis of COVID-19**

In a secondary analysis, in order to inform about the effectiveness to protect against asymptomatic and symptomatic infections, outcomes from the main analysis will be divided according to the symptoms recorded around the date of confirmed covid-19 in the patient PC eHR. Two effectiveness parameter, i.e. to protect against asymptomatic and asymptomatic infection, will be estimated separately for each vaccine. The date of the COVID cases will be the 1st date the sample was taken for testing.

Cases of **Asymptomatic** infection will be defined as a positive test without recorded symptoms in primary care  $\pm$ 14days, hospitalisations/Intensive care unit (ICU) or hospital diagnosis of the date the sample was taken). In asymptomatic analysis, symptomatic infections will participate as non-cases stopping at covid date.

Cases of **Symptomatic** infection will be defined as a positive test with recorded symptoms in primary care  $\pm$ 14days of the date the sample was taken, or linked Hospitalisations/Intensive care unit (ICU) admissions. In symptomatic analysis, asymptomatic infections will participate as non-cases stopping at covid date.

Note: In epidemiological vigilance protocols, among asymptomatic patients, isolation must be maintained till 10 days after the date when the sample was taken. For a sensitive approach we will broaden till 14 days in order to allow for delayed records in PC eHR.

\*Note: some misclassification may be present since patients with mild disease (mild symptoms) may never seek care that will be assumed as asymptomatic.

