### **9.3.3.3 Severe COVID-19 Hospitalisation for COVID-19**

In a secondary analysis, the outcome will be incident covid-19 infections resulting in an admission or discharge diagnosis to hospital (inpatient record) or intensive care unit as the setting of care. Admissions will be identified through linked (at anytime) with the test result or within  $\pm$ 14days of the date the sample was taken (if hospitalisation was recorded in primary care clinical profile). Those type of identification will depend on the region providing the data to BIFAP. If not available for all regions, restriction to regions will be performed.

The date of the outcome will be the admission date.

In that analysis, remaining non-severe covid-19 infections will participate as non-cases stopping at covid date.

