### **9.7.3 Comparative Analysis**

#### **9.7.3.1 Estimation of Vaccine Effectiveness**

Cox proportional hazards regression, yielding a hazard ratio (HR; 95%CI), accounting for censoring, changing incidence over time, and competing risks (Section 9.7.3.3) will be estimated for the defined periods: i.e. 0 to 14 days after D1, 15 after D1 until D2, 0 to 14 days after D2 and 15-90 days, 91-180 days, and  $\geq 181$  days after D2 in comparison with similar followed periods from time zero in the unvaccinated group.

This method will calculate a single vaccine effectiveness measure for each period of observation (assumed constant over those defined periods) in vaccinated versus unvaccinated groups. Crude vaccine effectiveness will be calculated for all the outcomes as 1 minus HR.

The assumption of proportionality of the survival curves in the vaccinated and unvaccinated groups will be evaluated.

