#### **9.7.3.2 Adjustment for Confounding**

Backward stepwise selection method will be used to identify variables associated with each outcomes according to a level of significance ( $p\text{-exit} \geq 0.1$ ,  $p\text{-entry} < 0.05$ ) for inclusion or exclusion, that could confound the effectiveness estimates and thus adjust the final models.

Confounders will be measured at baseline and updated before each vaccine dose is administrated or every 28 days (in order to update the collection of confounders during the follow-up of both, vaccinated and unvaccinated patients). The adjusted vaccine effectiveness for all the outcomes will be estimated as 1 minus the adjusted HR.

Adjusted time-specific RDs (e.g., RD at 3, 6, 9, 12 months after time zero) will also be tested [38]

Patients receiving one type of vaccine who receive later a dose of another COVID-19 vaccine, will be considered switcher from the date that the last dose was received and analysed as switchers, since such censoring/switch can be informative. Among switchers, each combination of vaccines will be analysed separately.

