#### **9.7.3.3 Competing Risk Analysis**

Events (e.g., death due to causes other than COVID-19) that may make it impossible for the event of interest to occur (e.g., hospitalisations for COVID-19) act as competing events in the analysis of certain outcomes. The relevance of competing events increases when the study population is old or sick (a plausible target population of the COVID-19 vaccine) or when the follow-up is long. The use of specific methodology to handle competing events can help in the accurate interpretation of the study results.

Thus, competing risk in survival analysis will be taken into account in an additional HR estimation.

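### Cumulative incidence is planned as 1 minus Kaplan-Meier with competing events censored, while the competing-risk method is applied only to hazard ratios, so stated absolute risks will be somewhat too high

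*Protocol*

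**What the plan says.** Five places in the protocol bear on this.

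- **Absolute-risk curves (9.7.2).** The estimator is fixed: "cumulative incidence curves (1 minus the Kaplan–Meier risk) for outcomes will be estimated to visualise the occurrence of COVID-19 outcomes over time since time zero".
- **End of follow-up (9.3.1).** The stop date is built from "covid-19 infection, death, loss to follow-up and end of study period". Death stands beside loss to follow-up and administrative end.
- **Split outcomes (9.3.3.2, 9.3.3.3).** "In asymptomatic analysis, symptomatic infections will participate as non-cases stopping at covid date", with a mirror rule for the symptomatic outcome. For hospitalisation, "remaining non-severe covid-19 infections will participate as non-cases stopping at covid date".
- **Competing risks (9.7.3.3, 9.7.3.1).** Section 9.7.3.3 counts non-COVID death among events that can make the outcome impossible and adds that "The relevance of competing events increases when the study population is old or sick". Its remedy is that "competing risk in survival analysis will be taken into account in an additional HR estimation". Section 9.7.3.1 describes the main Cox hazard ratio as already "accounting for censoring, changing incidence over time, and competing risks (Section 9.7.3.3").
- **Risk differences (9.7.3.2).** "Adjusted time-specific RDs (e.g., RD at 3, 6, 9, 12 months after time zero) will also be tested". The reference cited is the one cited for the curves. No estimator is named.

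No section plans a cumulative incidence function. Section 9.1 names effect measures on the absolute scale as an aim of the design.

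**The concern.** The plan identifies the competing-risk problem and then corrects the quantity that needs it least. A cause-specific Cox hazard ratio may legitimately censor competing events, and 1 minus that ratio is a valid effectiveness measure. The complement of a Kaplan-Meier curve is different. With deaths and other-type infections censored, it estimates risk in a setting where those events cannot happen. It does not estimate the proportion of the cohort that will have the outcome. Since 1 minus Kaplan-Meier can never fall below the true cumulative incidence, the error has a known direction for each curve.

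At stake are the absolute risks shown to readers, chiefly in the subgroups of Section 9.7.4.1 with high background mortality (age 80 and over, cancer, cardiovascular disease). Any risk differences taken from the same curves would also be affected. Separate curves for symptomatic and asymptomatic infection would also add up to more than the curve for all infections.

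**Working it through.** **Plan's own figure.** The protocol states no cumulative incidence or risk difference. Its only usable input is the risk in Section 9.5: 60.57 per 100,000 in 14 days = 0.0006057, as in Table 1. Table 1's probabilities of 1 reproduce but have no bearing on this point.

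**Inputs**
- Infection hazard, held constant (assumption): λ = −ln(1 − 0.0006057)/14 = 4.328 × 10⁻⁵ per day, about 0.0158 per year.
- Non-COVID death: not given in the protocol. Assumed hazard 0.01 per year for general adults. Assumed annual mortality m of 6%, 10% and 15% for elderly or ill groups, with μ = −ln(1 − m)/365, that is 0.0619, 0.1054 and 0.1625 per year.

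**Formulas**
- 1 minus Kaplan-Meier with death censored: 1 − exp(−λt).
- Cumulative incidence: λ/(λ+μ) × [1 − exp(−(λ+μ)t)].
- Scale: SE = √[CIF(1 − CIF)/n], with n = 100,000 chosen only for illustration.

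**Unvaccinated cumulative incidence**

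| Time | 1−KM | CIF, m = 6% / 10% / 15% | Relative excess | Excess in SE, m = 6% to 15% |
|---|---|---|---|---|
| 90 days | 0.389% | 0.386 / 0.384 / 0.381% | 0.8 / 1.3 / 2.0% | 0.15 to 0.39 |
| 180 days | 0.776% | 0.764 / 0.756 / 0.746% | 1.5 / 2.6 / 4.1% | 0.4 to 1.1 |
| 365 days | 1.567% | 1.520 / 1.488 / 1.447% | 3.1 / 5.3 / 8.3% | 1.2 to 3.2 |

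For general adults (death hazard 0.01 per year) the 12-month figures are 1.567% against 1.559%, an excess of 0.5%. The largest absolute gap in the table is 1.567 − 1.447 = 0.12 percentage points.

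**Split outcomes.** Assume 60% of infections are symptomatic and there is no death. At 180 days the two 1−KM curves give 466.3 + 311.1 = 777.4 per 100,000, against 776.0 for all infections. The excess is about 1.5 per 100,000, or 0.19%.

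**Risk differences at 12 months, if taken from these curves** (per 100,000; year of 365.25 days; RR 0.05 and 0.331 from Table 1, 0.70 assumed)

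| RR | Death hazard, unvaccinated / vaccinated | From 1−KM | From CIF | Error |
|---|---|---|---|---|
| 0.05 | 0.10 / 0.10 | 1489.3 | 1417.4 | +5.1% |
| 0.331 | 0.15 / 0.10 | 1046.4 | 960.0 | +9.0% |
| 0.331 | 0.05 / 0.20 | 1046.4 | 1056.8 | −1.0% |
| 0.70 | 0.05 / 0.20 | 467.9 | 532.3 | −12.1% |

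With equal death hazards and positive effectiveness, the difference is overstated by about the same percentage as the risk. With low effectiveness and higher competing mortality in the vaccinated, the sign reverses.

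**The case against.** The strongest reply is that the curves are descriptive. Effectiveness is 1 minus HR and does not use them. Section 9.7.2 also plans person-year rates with confidence intervals, which carry no Kaplan-Meier error and could supply an incidence difference. All of this stands and limits the weight of the point.

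Second, risk with competing death removed is a recognised target. It would be a fair defence if the protocol declared it. Instead, Section 9.7.2 wants the curves to show how outcomes occur over time, and Section 9.7.3.3 treats death as making the event impossible. The curves therefore do not deliver their stated purpose.

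Third, long horizons flatter the size. The study period starts on 21 December 2020 and the milestones put data collection at end of June to July 2021, which allows about 6 to 7 months. Twelve months, although named for the risk differences, would need later extractions. At 90 days the excess stays below half an SE with 100,000 people. This also stands. SE multiples based on all 709,676 people aged 80 and over (317,844 + 246,643 + 145,189) should not be used, because they would place everyone in one uncensored arm while comparators move to the vaccinated group.

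A reader might infer two stronger claims. One is that the planned risk differences are overstated. Section 9.7.3.2 names no estimator, a shared citation is not one, and the error can reverse. The other is that competing risks reach only a supplementary HR. Section 9.7.3.1 says the main HR accounts for them too. The text supports only that the method reaches hazard ratios and not absolute risks.

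**Conclusion.** The point holds as a minor, cheaply corrected flaw. As written, cumulative incidence will be overstated for every outcome except all-cause mortality, where no other death competes. That exception assumes death from any cause is counted. Section 9.3.3.5 ties the outcome to 8 weeks after the COVID date, and under that restriction deaths outside the window would compete.

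The relative excess is about 0.5% at 12 months in general adults. In elderly or ill groups it is roughly 1.5-4% at 180 days and 3-8% at 12 months. These figures rest on a constant rate from Section 9.5 and on assumed mortality, since the protocol gives none. Risk differences are at risk of bias, usually but not always upward, only if derived from the same curves. Effectiveness estimates and person-year rates are unaffected.

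**What to change.** 1. In Section 9.7.2, replace the Kaplan-Meier complement with the Aalen-Johansen cumulative incidence function for every outcome except all-cause mortality. Take non-COVID death as a competing event and, for the split outcomes, the other infection type as well.
2. In Section 9.7.3.2, state that the risk differences are derived from these functions.
3. Reconcile Sections 9.7.3.1 and 9.7.3.3: vaccine effectiveness is 1 minus the cause-specific HR, and any subdistribution HR is supportive only.

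No new data are needed, because dates of death and infection are already collected. The cost is a few sentences of protocol text, a little more analysis work and slightly lower stated absolute risks.
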